### 2.4.4 Cost-effectiveness Objective

To estimate the cost-effectiveness of APRV compared to conventional lung protective ventilation.

### 2.5 Eligibility criteria

Our eligibility criteria will enrol a population clinically and pragmatically likely to benefit from the intervention. Our exclusion criteria are designed to ensure early use of APRV, inclusion of a population of critically ill patients with moderate to severe AHRF most likely to benefit, and exclusion of patients unlikely to benefit due to their underlying condition or at increased risk of a complication from the intervention.

Patients who meet all the following inclusion criteria and none of the exclusion criteria are eligible to participate in the trial.

### 2.5.1 Inclusion criteria

- 1. Age ≥ 18 years
- 2. Receiving invasive mechanical ventilation
- Moderate to severe AHRF (PaO2/FiO2 <20kPa with Positive End Expiratory Pressure (PEEP) ≥5 cmH2O) assessed at time of screening (or as documented in the medical record in the preceding 2 hours)
- 4. Expected to stay on invasive mechanical ventilation for >48hrs

### 2.5.2 Exclusion criteria

- 1. Receiving IMV ≥ 60 hours at time of screening as will be unable to deliver early APRV
- 2. Primary reason for invasive mechanical ventilation is one of the following:
  - a) Asthma
  - b) Severe COPD
  - c) Pulmonary embolism (massive or sub-massive) (as cause of hypoxaemia is not primarily due to collapse of lung tissue)
  - d) Existing neuromuscular disease such as Motor Neurone Disease, Guillain Barre or Myasthenia Gravis (as the cause of respiratory failure is not primarily lung-related)

- 3. Refractory shock (systolic blood pressure < 90 mmHg, despite fluid administration and vasoactive drugs)\*
- Severe hypercapnic respiratory acidosis (pH <7.20 on the arterial blood gas assessed for trial inclusion)\*
- 5. Ongoing air leak (e.g. unresolved pneumothorax at time of screening)\*
- 6. Traumatic brain injury with uncontrolled intracranial hypertension\*
- 7. Likely death or treatment withdrawal in next 24 hours
- 8. Home ventilation or home oxygen therapy prior to admission
- \*(patients can be recruited if this resolves and remain eligible).

### 2.6 Participant identification / Screening

All ventilated CCU patients will be screened daily for eligibility by the CCU nursing or medical staff. Each site will maintain a screening log which will include data on the numbers of patients potentially meeting eligibility criteria but not entered into the trial, those for which consent is given but are then not randomised, numbers not meeting inclusion criteria and reasons for non-enrolment. A fully anonymised patient-level minimal dataset (including age, sex, ethnicity, and reasons for nonenrolment) will be recorded to establish an unbiased trial population and for reporting according to the CONSORT statement [27,28].

### 2.7 Informed consent

It is the responsibility of the Principal Investigator (PI) (or designee) to ensure that written informed consent is obtained for each participant prior to entry into the trial. Consent may be obtained by the PI; or an appropriately trained member of the research team provided they are GCP trained, suitably qualified and experienced and have been delegated this duty by the Principal Investigator on the delegation log.

Patients will be unable to give informed consent because of sedation, infection, delirium and mechanical ventilation. Consent will therefore be obtained in line with the legal requirements for obtaining consent in patients without capacity and a personal or professional consultee will be approached.

For centres in Scotland, if there is a person willing and able to take on the responsibilities of Welfare Guardian/Nearest Relative, they will provide consent for inclusion. In cases where no Welfare Guardian/Nearest Relative is available it will not be legally possible to enrol the patient (specific to the Adults with Incapacity Act Scotland for non-CTIMP trials).

Further details on the consent process are detailed in section 4.2.3 of the CoReCCT master protocol.

Once a participant who initially lacks capacity, regains capacity, they will be informed about the trial and invited to consent to continue in the trial. There is no requirement to reaffirm consent in Scotland.

### 2.8 Randomisation

### 2.8.1 Randomisation

Randomisation will occur once eligibility has been confirmed and consent obtained. Participants will be randomised via randomly permuted blocks using an automated web-based system on a one-toone basis, stratified by site and prior enrolment into the Awake Prone Positioning and Protect Airways trials, using a computer-generated randomisation schedule managed by the Warwick CTU. We have selected a parallel group RCT design to minimise selection bias and ensure against accidental bias.

### 2.8.2 Post-randomisation withdrawals

Participants (or their legal representative) are free to withdraw or discontinue from the trial at any time, without having to give a reason. Withdrawing from the trial will not affect them or their care in any way. Where participants have given consent, the research team will keep information already collected prior to withdrawal, unless specified by the participant. Participants may also be asked for permission to collect further outcome data from their medical records or data linkage. Where participants regain capacity to consent and then choose to withdraw, participants will be asked if they are happy for data collected prior to withdrawal to be kept.

### 2.9 Trial intervention

### 2.9.1 Intervention arm (APRV protocol)

We will compare APRV to standard lung protective IMV. All commercially available ventilators used in the NHS can provide APRV. APRV is a method of IMV which uses longer inspiration times followed by a brief expiration. The longer inspiration time enables alveolar recruitment and oxygenation while the short expiration time maintains lung volume. This reduces shear-stress damage to the alveoli, whilst maintaining adequate ventilation.

APRV has four main control settings. Two of which determine the inspiratory cycle: inspiratory or high pressure ( $P_{high}$ ) and inspiratory time, or time at high pressure (Thigh). The inspiratory phase is also known as continuous positive airway pressure (CPAP) Phase. The other two control settings determine the expiratory cycle: expiratory or low pressure ( $P_{low}$ ) and expiratory or time at low pressure ( $T_{Low}$ ) which make up the expiratory or Release Phase.

In accordance with current clinical practice for APRV, expiratory time will be individualised for each patient based on their respiratory mechanical characteristics, which will vary during the course of the disease. Inflation pressures during inspiration will be adjusted to maintain tidal volumes within lung protection ranges.

### 2.9.2 Initial APRV Settings

### Phigh (inspiratory Pressure)

To transition a patient to APRV, a volume control mode, the  $P_{HIGH}$  will be set to equal to the plateau pressure ( $P_{PLAT}$ ), or to the peak inspiratory pressure (PIP) if transitioned from a pressure control or ventilation mode.

For patients who receive APRV immediately following intubation, set the  $P_{high}$  starting at 25 cmH2O. Then titrated upwards or downwards by 1-2 cmH2O increments or decrements aiming to values between 20 and 30 cmH2O, so to achieve minimum tidal volumes > 4-5 mL/Kg predicted body weight (PBW).

 $\mathsf{P}_{\mathsf{low}}$ 

The Set the  $P_{low}$  to 0 cmH2O.

 $\mathsf{T}_{\mathsf{low}}$ 

[figure not shown]
Use an initial  $T_{low}$  of 0.5 seconds for 1-3 breaths. Then using the ventilator "freeze waveform" function, it is possible to quantify the PEF. The  $T_{low}$  can then be adjusted so that the  $T_{EF}$  is 75% of the PEF. A  $T_{low}$  that is too long may decrease the end-expiratory pressure leading to derecruitment and atelectrauma. A  $T_{low}$  that is too brief may cause overinflation and volutrauma.

 $\mathsf{T}_{\mathsf{high}}$ 

Set the  $T_{HIGH}$  by dividing the respiratory rate by 60 and then subtracting the  $T_{LOW}$ . When transitioning to APRV, a  $T_{high} < 4$  seconds may be needed initially to maintain the respiratory rate (RR) and tidal volume (i.e., minute ventilation - VE) close to that of the conventional ventilation mode used before transition. This is because APRV may initially drop the VE resulting in hypercapnia if the  $T_{high}$  is set between 4-6 seconds and the lung has not yet recruited to sufficiently exchange CO2.

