### 2.9.2.1 Transition to APRV

### Figure 3: Transition to APRV

### Table 3: Initial Settings

Adjustment to settings is based on minute ventilation (VE), slope angle, and arterial blood gases
---

	From Volume Control Mode	From Pressure Control Mode	From Dual Targeted Mode		
P High (cmH 2 O)*	Equal to plateau pressure	Equal to peak pressure	Equal to peak pressure		
P Low (cmH 2 O)	0	0	0		
Т ніgh (seconds)**	Set using the respiratory rate prior to APRV transitioning. using this formula: $T_{high} = (60/current rate) - T_{Low}$ i.e., rate 26; (60/26) = 2.3 - $T_{Low}$ of 0.5 = $T_{High}$ of 1.8 seconds				
$T_{Low}$ (seconds)*** set to $E_{FT}/E_{FP}$ of 75%. NOTE : These ranges are a starting point and may require adjustment to achieve $E_{FT}/E_{FP}$ of 75%.	0.4-0.6	0.4-0.6	0.4-0.6		

\*A PHigh >30 cmH2O may be required depending on body habitus and increased chest wall elastance.

\*\* When transitioning to APRV, Vt typically decreases to <6mL/kg resulting in a lower VE. In this case, increase the VE by decreasing the THigh to achieve or exceed previous VE.

DO NOT increase VE by increasing the  $T_{Low}$  (unless EFT/EPF is >75, i.e., not optimised) as this will decrease alveolar stability. If Vt is <3mL/kg consider increasing  $P_{High}$  or a combination of increased  $P_{High}$  and decreased  $T_{High}$ . As the lung recruits (compliance improves), VE requirements decrease allowing the  $T_{High}$  to be increased.

\*\*\*These are ranges for initial  $T_{Low}$  settings. The  $T_{Low}$  setting that achieves EFT/EFP of 75% may be higher or lower than these initial suggested ranges.

Table 4: Rationale for	Selected Settings
------------------------	-------------------

Setting	Rationale
P High	Before transitioning to APRV assess intravascular status to determine preload dependency.
P Low	A P Low of 0 cmH 2 O will not result in alveolar instability and collapse if the T Low is set to terminate ( $E_{FT}$ ) at 75% of the expiratory flow peak ( $E_{FP}$ ) ( $E_{FP} \times 75\% = E_{FT}$ ).

	A $P_{Low} > 0$ cmH 2 O can increase PCO 2 and has a negative effect on secretion removal.
	The $T_{High}$ controls bulk rate (convective) and alveolar (diffusive) ventilation.

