### 2.9.2.5 Weaning APRV

Once a patient's clinical condition has improved, clinicians will follow a protocol to wean a patient using APRV that does not involve switching mode to pressure support ventilation, which is the weaning mode most commonly used as standard care.

Once improved (FiO2  $\leq$  40%, SpO2 92-95% and able to sustain spontaneously breathing at a comfortable rate (i.e., 10-30 bpm), APRV should be weaned as follows:

- 1. Progressively increase the inspiratory time ( $T_{high}$ ) by 0.5-1s steps until  $T_{High} > 6$  seconds; and wean the  $P_{HIGH}$  by in 2 cmH2O increments as tolerated to a  $P_{HIGH of}$  15 cmH2O.
  - a. Monitor for desaturation, increased work of breathing, or tachypnea
  - b. When the patient reaches a  $P_{HIGH of}$  10-12 cmH2O, patient can be transitioned to CPAP 10-12 cmH2O without pressure support (PS = 0 cmH2O) and undergo checks for extubation

Participants must continue to receive APRV until extubation to maximise the APRV "dose" received. Remember to optimise sedation to promote more spontaneous breathing.

60	P HIGH = Up or Down –Titrate by 1-2 cmH 2 O to maintain V T >4 and <10ml/kg	Monitor
Weaning	T HIGH + 0.5-1.0 s increments Every 1-2 hours until T high up to 30s Transition to CPAP Optimise Sedation to allow progressively more spontaneous breathing	
 
P0.1
 
ΔPocc
 
RSBI
 
Respiratory Pattern
 

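### Section 2.9.2 and Table 3 of the protocol give inverse rules for the starting T_high; on Table 3's own example they yield -0.07 s and 1.8 s

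*Protocol*

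**What the plan says.** **Starting T_high.** The narrative in protocol section 2.9.2 (Initial APRV Settings) has it set "by dividing the respiratory rate by 60 and then subtracting the" T_low. The same section starts T_low at a value "of 0.5 seconds for 1-3 breaths". It also says that a T_high below 4 "seconds may be needed initially to maintain the respiratory rate (RR) and tidal volume", and it mentions 4-6 s as the range that may be too long at first.

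Table 3 (section 2.9.2.1) gives T_high as 60 over the current rate, minus T_low. It works an example, "rate 26; (60/26) = 2.3", then subtracts a T_low of 0.5 to reach 1.8 s. Its starting range for T_low is 0.4-0.6 s in all three columns.

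**Weaning (section 2.9.2.5).** The numbered text raises T_high "by 0.5-1s steps until" it exceeds 6 s, and lowers P_high to 15 cmH2O. Item b then allows a move to CPAP once P_high is 10-12 cmH2O. The weaning panel in the same section raises T_high by "increments Every 1-2 hours until T high up to 30s" and then mentions the transition to CPAP.

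**The concern.** The two starting rules share the subtraction of T_low but invert the ratio in front of it. Both stand in current operative text and both are addressed to the clinician at the ventilator, so this is not background wording that can be left alone.

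What is at stake is consistent delivery of the experimental arm. About 40 units will take part, and the subgroup plan in section 6.3 provides for sites with no previous APRV experience. Such sites depend most on the written rule. Section 2.10.1 feeds fidelity data back monthly and closes sites with persistent problems, so the reference text should give one answer.

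The weaning passage raises a milder question of the same kind: a reader cannot tell from the text and the panel together at which T_high, or by what step in P_high, APRV gives way to CPAP.

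**Working it through.** **Inputs.** Rate 26/min and T_low 0.5 s come from Table 3's example. T_low 0.5 s is also the initial value in the section 2.9.2 narrative. The T_low range of 0.4-0.6 s is from Table 3. The other rates below are illustrative.

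**Step 1: reproduce the plan's figure.** Table 3 rule: T_high = 60/rate - T_low = 60/26 - 0.5 = 2.308 - 0.5 = 1.808 s. This agrees with the printed 1.8 s.

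**Step 2: narrative rule on the same inputs.** T_high = rate/60 - T_low = 26/60 - 0.5 = 0.433 - 0.5 = -0.067 s.

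**Step 3: other rates, T_low 0.5 s.**

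| Rate (/min) | Table 3 rule (s) | Section 2.9.2 narrative (s) |
|---|---|---|
| 10 | 5.50 | -0.33 |
| 15 | 3.50 | -0.25 |
| 20 | 2.50 | -0.17 |
| 26 | 1.81 | -0.07 |
| 30 | 1.50 | 0.00 |
| 35 | 1.21 | 0.08 |

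**Step 4: sensitivity to T_low at rate 26.** For T_low 0.4, 0.5 and 0.6 s, Table 3 gives 1.91, 1.81 and 1.71 s. The narrative gives +0.03, -0.07 and -0.17 s. The negative sign therefore belongs to the example as stated; at T_low 0.4 s the narrative result is positive, but only 0.03 s.

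**Step 5: where the narrative rule reaches zero.** Setting rate/60 = T_low gives rate = 60 x T_low, which is 24, 30 and 36/min for T_low 0.4, 0.5 and 0.6 s. Below that rate it is negative.

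**Step 6: where the rules agree.** rate/60 = 60/rate only when rate squared = 3600, that is at 60/min. Rounding or choice of T_low cannot reconcile them at the rates tabulated above.

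**Step 7: weaning, side by side.**

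| Source in section 2.9.2.5 | T_high | P_high |
|---|---|---|
| Numbered text, step 1 | raised until above 6 s | lowered to 15 cmH2O |
| Numbered text, item b | not stated | CPAP possible at 10-12 cmH2O |
| Weaning panel | up to 30 s, CPAP mentioned next | titrated to tidal volume |

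A T_high of 10 s, for example, satisfies both the text and the panel. The move from 15 to 10-12 cmH2O is not described.

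**The case against.** On the starting rule, the best defence is that it will do little harm. A negative time cannot be entered on a ventilator, so in the protocol's own example the error shows itself. The surrounding paragraph speaks of T_high in whole seconds, and Table 3 gives an explicit formula with a worked example. The value is only a start, since Table 3's notes adjust it to minute ventilation. Sites complete an APRV training package before opening (section 2.9.4.4) and are mentored (section 2.2). All of this stands as an argument about likelihood of harm, and a reader who infers that patients will in fact be ventilated on the wrong setting goes further than the documents allow. It does not remove the contradiction, and where the narrative rule is positive (0.08 s at 35/min with T_low 0.5 s) the impossible sign no longer gives a warning.

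On weaning, the objection largely succeeds. Above 6 s is a floor and up to 30 s is a ceiling, so they overlap. P_high 15 and then 10-12 can be successive stages, and item b is permissive. The panel's layout was lost in text extraction, so its order relative to the CPAP step is uncertain.

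Two stronger readings are tempting:

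- **That weaning differs by 24-96 h between sites, against a target effect of 2 days.** The step count is right: (30 - 6)/1.0 = 24 steps at 1 h, up to (30 - 6)/0.5 = 48 steps at 2 h. As a difference in ventilation time it needs one group to stop at 6 s and go straight to CPAP, the other always to reach 30 s, and P_high weaning to add no time. The documents state none of these, and the numbered text ties CPAP to P_high, for which it gives no interval.
- **That adherence cannot be judged.** Section 2.9.5 leaves that definition to the statistical analysis plan, which is not at hand. Nothing shows that it will depend on the starting T_high or on the final weaning T_high.

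**Conclusion.** The contradiction on the starting T_high is established by arithmetic on the protocol's own numbers: 1.8 s from Table 3 and -0.07 s from the section 2.9.2 narrative. With T_low 0.5 s the narrative rule is zero or negative at all rates up to 30/min. The only assumption is that the narrative is read literally. It should be corrected because it is an operative instruction for the trial intervention, even though training and the worked example make a bedside error less likely.

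The weaning point is a request for clarification with lower confidence. The passages may be compatible, so no effect on ventilation duration, the primary outcome or power is claimed. Nothing here bears on the sample size or error rates. Which rule or end point is clinically right is for the clinical leads.

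**What to change.** - The clinical leads reconcile the T_high rule in section 2.9.2 with the one in Table 3, and the single agreed rule goes into the text, table, figures and training material.
- They also reconcile section 2.9.2.5 with its weaning panel. It should be clear whether the two T_high values are a floor and a ceiling or competing end points, and how P_high gets from the end of step 1 to the level named in item b.

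The cost is a short protocol correction and a reissue of the affected training material. Design, sample size and analysis do not change.

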### 2.9.2.1 Transition to APRV

### Figure 3: Transition to APRV

### Table 3: Initial Settings

Adjustment to settings is based on minute ventilation (VE), slope angle, and arterial blood gases
---

	From Volume Control Mode	From Pressure Control Mode	From Dual Targeted Mode		
P High (cmH 2 O)*	Equal to plateau pressure	Equal to peak pressure	Equal to peak pressure		
P Low (cmH 2 O)	0	0	0		
Т ніgh (seconds)**	Set using the respiratory rate prior to APRV transitioning. using this formula: $T_{high} = (60/current rate) - T_{Low}$ i.e., rate 26; (60/26) = 2.3 - $T_{Low}$ of 0.5 = $T_{High}$ of 1.8 seconds				
$T_{Low}$ (seconds)*** set to $E_{FT}/E_{FP}$ of 75%. NOTE : These ranges are a starting point and may require adjustment to achieve $E_{FT}/E_{FP}$ of 75%.	0.4-0.6	0.4-0.6	0.4-0.6		

\*A PHigh >30 cmH2O may be required depending on body habitus and increased chest wall elastance.

\*\* When transitioning to APRV, Vt typically decreases to <6mL/kg resulting in a lower VE. In this case, increase the VE by decreasing the THigh to achieve or exceed previous VE.

DO NOT increase VE by increasing the  $T_{Low}$  (unless EFT/EPF is >75, i.e., not optimised) as this will decrease alveolar stability. If Vt is <3mL/kg consider increasing  $P_{High}$  or a combination of increased  $P_{High}$  and decreased  $T_{High}$ . As the lung recruits (compliance improves), VE requirements decrease allowing the  $T_{High}$  to be increased.

\*\*\*These are ranges for initial  $T_{Low}$  settings. The  $T_{Low}$  setting that achieves EFT/EFP of 75% may be higher or lower than these initial suggested ranges.

Table 4: Rationale for	Selected Settings
------------------------	-------------------

Setting	Rationale
P High	Before transitioning to APRV assess intravascular status to determine preload dependency.
P Low	A P Low of 0 cmH 2 O will not result in alveolar instability and collapse if the T Low is set to terminate ( $E_{FT}$ ) at 75% of the expiratory flow peak ( $E_{FP}$ ) ( $E_{FP} \times 75\% = E_{FT}$ ).

	A $P_{Low} > 0$ cmH 2 O can increase PCO 2 and has a negative effect on secretion removal.
	The $T_{High}$ controls bulk rate (convective) and alveolar (diffusive) ventilation.
T High	Using a $T_{High}$ of 4-6 seconds is typical with elective APRV use. If used as a rescue strategy, a shorter $T_{High}$ is required to provide more bulk ventilation until the lung has recruited and stabilized.
	NOTE: If the Vt drops below 3 mL/kg, it may be necessary to decrease $T_{High}$ and increase $P_{High}$ to maintain or exceed pre-transition VE.
	The $T_{Low}$ is the duration of the release phase and controls the amount of airway pressure ( $P_{High}$ ) and lung volume released.
T Low	During the release phase, expiratory gas flow through the artificial airway creates a slope angle of deceleration. The resultant slope angle is analyzed as this reflects mechanical properties of the respiratory system. Although the release phase is protocolized to $E_{FT}/E_{FP}$ of 75%, the time to achieve 75% is personalized to the patient and the time course of their respiratory mechanics. The $E_{FT}/E_{FP}$ of 75% has been clinically and experimentally validated to optimize alveolar stability.

### 2.9.2.2 Challenges potentially encountered during transitioning to APRV

Hypotension

Transitioning from a conventional ventilation mode to APRV may result in transient hypotension. This may be due to unrecognized hypovolemia despite an acceptable blood pressure prior to transition. Ensuring optimal volume status and a starting from a lower Phigh with cautious Phigh up-titration is generally sufficient to blunt the magnitude and duration of hypotension.

### Sedation

Sedation or use of neuromuscular blockade (if being administered) does not need to be modified prior to or during transition to APRV. Once transitioned, optimise analgesia for pain control and sedate as necessary to achieve ser Richmond Agitation Sedation Scale (RASS) target (e.g., RASS -2 to 0).

[figure not shown]
### 2.9.2.3 Optimising and Titrating APRV

The  $P_{high}$  requires titration over time in response to changes in lung volume and compliance. Titrate upwards or downwards by 1-2 cmH2O at a time to maintain VT > 4 mL/Kg PBW and <10 mL/Kg.

Optimize  $T_{High}$  by increasing by 0.5 to 2 seconds to maintain target PaCO2.

Titrate the fraction of inspired oxygen (FiO2) down to 40% while maintaining an oxygen saturation (SpO2) of 92-95%. If SpO2  $\leq$  90% despite FiO2  $\geq$  60%, consider increasing the Phigh in 2 cmH2O increments up to 35 cmH2O while monitoring haemodynamic status.

**S**pontaneous breathing on APRV can be introduced by weaning analgosedation when work of breathing is minimised (assess with P0.1 and f/VT).

